## **10.6 Safety Assessments**

At all visits, participants will be assessed for possible Adverse Events (AEs). All ongoing SAEs should be followed through to stabilisation or recovery. AEs that are possibly, probably or definitely attributable to the intervention will be reported via the eCRF as they occur (between consent and 26 weeks post brain injury). The investigator and designated study personnel will monitor each participant for AEs during the study.

AEs that meet the criteria for serious, are considered Serious Adverse Events (SAEs) and will be reported for the duration of the project. The investigator or designee will ask the participant non-leading questions in an effort to detect adverse events, important medical events and serious adverse events. Refer to section 13 of this protocol for detailed explanation.

## **11 Study intervention**

As with the control periods, the intervention periods will vary across sites, with some sites having 2.5 years, and some having 1 year in total. This will depend on site randomisation. The intervention will consist of two components – i) Cultural Security Training (CST) for hospital staff, and ii) introduction of an Aboriginal Brain Injury Coordinator (ABIC) at each site employed for one day/week.

### **11.1 Description of interventions**

#### **11.1.1 Cultural Security Training of hospital staff**

The CST will involve training of 20 health professionals at each site (nursing, medical and allied health staff). It will involve 3 hours face-to-face time delivered in person where possible or live via on-line platforms if constrained by extraordinary circumstances (such as hospital quarantine as per COVID-19 context), followed by 3 hours online focusing on issues surrounding brain injury. The face to face sessions will be co-facilitated by a local cultural security trainer and a member of the research team. The training will be undertaken to suit the individual site with alternative delivery sessions being one three hour block or 3 x 1 hour sessions and will be completed within a 3 week period. The online modules will constitute approximately 3 hours of study. This component must be completed within 3-4 weeks of completion of the face to face component. administered by Edith Cowan University

The training will be offered at each site every 6 months to address the issue of changing/rotating staff.

Details of the CST are outlined in the Intervention Protocol.

#### **11.1.2 Aboriginal Brain Injury Coordinator**

An Aboriginal person will be employed for one day/week at each of the project sites as an Aboriginal Brain Injury Coordinator (ABIC). The ABIC will see the participants in hospital and up till 26 weeks post injury onset and provide

education, support, liaison, and advocacy services to the participants and their families.

A minimum qualification of a Certificate 3 in a relevant health or community care subject of study will be required. Qualifications and experiences as an Enrolled or Registered Nurse or in Aboriginal Health Work will be highly desirable.

The ABIC will receive 12 hours of training from the Neurological Council of Western Australia (NCWA) and the research team. Each ABIC will be located either in the hospital, the local community controlled Aboriginal Medical Service (AMS), or offices of the NCWA as part of their community neurological nursing service, depending on the preference of each site. This person will be supported by the local AMS, the NCWA community nursing service, and the research project manager.

The ABIC will visit the person if admitted locally to hospital, and follow up with the person and their family at home/aged care facility for 26 weeks thereafter. In cases of transfer between sites in the study, the ABIC at the site of recruitment will be the primary contact with the participant. Follow up of participants will occur through phone or telehealth contact as agreed upon. However, if the ABIC services have commenced at the place to which the participant is transferred, then the local ABIC will see the participant there. Conversely, if there is no ABIC service at the site of recruitment, the participant will not receive ABIC services even if they are transferred to a hospital region where ABIC services have been introduced, as they are technically part of the control period of the original site.

Further detail of the ABIC's role is outlined in the Intervention Protocol.

Any deviation from the prescribed protocols will be reported as a protocol deviation.

## **11.2 Recording of interventions**

### **11.2.1 Cultural Security training:**

The dates of training, numbers in attendance, characteristics of attendees in terms of discipline, years professional experience, gender, age and ethnic background will be recorded in a database by the research team member involved in the site-training.

### **11.2.2 Aboriginal Brain Injury Coordinator**

The activities of the Aboriginal Brain Injury Coordinator that involve direct and indirect contact with participants will be recorded in the e-CRF.

Details to be recorded include: the date of the activity; nature (direct or indirect); modality of direct contact (in-person; telephone; video-conference); location of the participant during contacts; location of ABIC during contacts; the specific activities that occurred (assessment of needs; counselling; goal setting; attending appointments with participant; education to patient and family; making referrals, advocacy, liaison with social services; attendance at multi-disciplinary meetings; consultation with healthcare providers). When the

activity relates to direct participant contact, either face to face or via telephone/video-conference the length of the session should be recorded.

The ABIC will also make clinical notes relevant to care coordination activities with the participant in a participant specific file that is identified by a participant number and which will be kept in a locked cabinet at the ABIC's workplace (either the offices of the NCWA or the Aboriginal Medical Service). These files will also contain an action plan; documented goals; documents related to referrals made; written correspondence with health and support services. The contents of these files will be sent to the recruiting site for storage in the CRF at the recruiting site, at completion of the intervention period.

### **11.3 Intervention integrity**

Detailed information regarding the implementation of the CST and the ABIC role is essential to record whether these components are delivered as planned.

The following components of each aspect of the intervention will be recorded for intervention integrity purposes.

#### **11.3.1 Cultural Security Training**

Dates of training, adherence to content, staff attendance and face to face completion of the training will be recorded by the research team member involved in the site-training. Completion of the online training component will be recorded on the secure website containing the online materials

#### **11.3.2 Aboriginal Brain Injury Coordinator (ABIC)**

Completion of training of the ABIC will be recorded.

To ensure the ABIC role is implemented as prescribed, Redcap data entry related to the ABIC role will be monitored on a monthly basis. Feedback will be provided to the ABIC if data is missing or prescribed activities have not been performed. These monitoring activities will occur in conjunction with ongoing clinical supervision by NCWA and ECU. See further details in the Intervention Protocol

## **12 Process evaluation**

As well as data related to intervention integrity, data will be collected that will enable evaluation of potential causal and overall contextual factors related to the outcomes of the study, as recommended by MRC and as included in the TIDieR checklist. As the nature of the intervention is complex i.e. interacting components, careful monitoring of implementation and contextual factors, including those related to organisational attitudes, hospital staff, brain injury survivors, and ABICs will be undertaken.

### **12.1 Cultural Security Training**

Factors related to the impact of the CST including *staff satisfaction* with training, and *perceived usefulness* of training will be measured through evaluation questionnaires.

A questionnaire examining staff satisfaction with and impact of the face to face training will be completed at the end of the face to face training (see Appendix 2). An online

questionnaire examining satisfaction with and impact of the online training specifically as well as reflection on the overall program will be undertaken by staff at the completion of the online component (see Appendix 3).

As well as the Minimum Processes of Care Indicators monitored as part of the main secondary data collection (see Section 10.4), a brief questionnaire will be undertaken with all Aboriginal participants at 12 and 26 week post discharge that will incorporate ratings of their hospital and general rehabilitation service experiences in terms of cultural security (see Appendix 4). This data will provide information on how services were received – which parts worked well and which parts might need to be further improved.

## **12.2 Aboriginal Brain Injury Coordinator**

The implementation of the ABIC will be monitored through the data collected as described in Section 11.2.2. In addition, a brief questionnaire surrounding the Aboriginal participants' perceptions regarding the usefulness of the ABIC support will be completed at 12 and 26 weeks (see Appendix 5). Individual interviews with a subset of participants (n=10) exploring participants' satisfaction with the Aboriginal Brain Injury Coordinator service will be conducted at 26 weeks by an independent interviewer.

The ABICs will also be interviewed either during or at the completion of their employment in order to gain their reflections and perspective on the role (see Appendix 6). Informal interviews with NCWA and AMS personnel working with the ABIC will be undertaken to record attitudes and context relevant to implementation of this service. All documentation will be coded and qualitatively analysed to identify themes/issues that arise. Any deviation from the prescribed treatment protocol will be documented, along with reasons and context as part of the process evaluation.

Individual characteristics of the ABICs will be recorded in order to estimate potential effects of personal characteristics including age, gender, language group, qualifications and previous experience in health settings. Primary location of the ABIC will also be recorded e.g. regional vs metropolitan, AMS vs NCWA-based in order to gauge effects of geographical context.

Recruitment and turnover of ABIC staff will also be recorded.

## **12.3 Hospital and community context**

Ongoing descriptive information will be collected at each site related to the specific hospital context e.g. general staffing levels, staff turnover, policy changes, accreditation processes occurring. This information will be collected by the Project Manager through informal discussions with key staff, and through regular Partner meetings (4 per year) where the general progress of the trial will be discussed, along with any such factors perceived to be influencing service delivery at the site. Content of these meetings will be recorded in detailed meeting minutes. In addition, the Project Manager will collect contextual information specific to the local community e.g. community activities available beyond formal hospital services e.g. yarning groups, social groups, location of AMSs within regions involved.

### **13 Adverse Events (AE) and Serious Adverse Events (SAE)**

The investigator is responsible for the detection and documentation of events meeting the criteria and definition of an adverse event as detailed below (AE) or a serious adverse event (SAE) as provided in this protocol. During the study, when there is a safety evaluation, site staff will be responsible for detecting AEs and SAEs, as detailed in this section of the protocol.

#### **13.1 Definition of an Adverse Event (AE)**

An Adverse Event (AE) is any untoward medical occurrence in any participant involved in the study. It does not necessarily have to have a causal relationship to the study intervention. However, for the purposes of this study, only those events which are possibly, probably or definitely attributable to the intervention will be noted.

Examples of an AE **include**:

- Exacerbation of a chronic or intermittent pre-existing condition including either an increase in frequency and/or intensity of the condition.
- New conditions detected or diagnosed after involvement in the study even though it may have been present prior to the start of the study.

Examples of an AE **do not include** a/an:

- Medical or surgical procedure (e.g. endoscopy, appendectomy); the condition that leads to the procedure is an AE.
- Situations where an untoward medical occurrence did not occur (social and/or convenience admission to hospital).

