	introduction of an Aboriginal Brain Injury Coordinator who will meet the participant whilst in hospital and follow up for 26 weeks with consultation, advocacy and support.
Safety Parameters/analysis:	Adverse events and serious adverse events will be collected for all participants. An independent safety monitoring committee will review all events on a regular basis and will report safety issues to the management committee. The committee will advise if the trial needs to be stopped if there is clear evidence of benefit or that the intervention is causing harm to participants.
Sample Size Determination:	We will require a total of 312 participants to detect a difference of 15 points on the EuroQoL-5D VAS with 80% power at the 5% significance level.

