### **13.3 Time Period, Frequency, and Method of Detecting AEs and SAEs**

All SAEs will be recorded from the time of consent until the final follow up visit at week 26.

Other adverse events possibly, probably, or definitely attributable to the intervention will be recorded from the time of consent until the final follow up visit at week 26.

Each participant will be monitored regularly by the site investigator and study personnel for events occurring throughout the study. During the period in hospital, the site investigator will enquire about AEs by asking the following non-leading questions:

*“How are you feeling?”*

At subsequent scheduled intervals participants will be asked:

*“Since you were last asked, have you felt unwell or different from usual?”*

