### 13.6.2 Assessment of Causality

The blinded assessor is obligated to assess the relationship between study treatment and the occurrence of each AE/SAE. The blinded assessor will use clinical judgment to determine the relationship. Alternative causes, such as natural history of the underlying diseases, concomitant therapy, other risk factors, and the temporal relationship of the event to the treatment period will be considered.

The causal relationship to the study treatment assessed by the blinded assessor should be assessed using the following classifications:

- Not Related** In the Assessors opinion, there is not a causal relationship between the study product and the adverse event.
- Unlikely** The temporal association between the adverse event and study treatment is such that the study treatment is not likely to have any reasonable association with the adverse event.
- Possible** The adverse event could have been caused by the study treatment.
- Probable** The adverse event follows a reasonable temporal sequence from the time of study treatment, abates upon discontinuation of treatment and cannot be reasonably explained by the known characteristics of the study participant’s clinical state.
- Definitely** The adverse event follows a reasonable temporal sequence from the time of study treatment start or reappears when study treatment is reintroduced.

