### *1. Safety*

Adverse events are expected to have a Poisson or negative binomial distribution. The distribution will be examined and the appropriate regression models will be used to compare counts of serious adverse events between conditions. Logistic regression will be used to compare binary adverse events (e.g. death). Risk ratios will be adjusted as per primary analysis with age, and mRS included as covariates.

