### *5. Interim analyses*

The DSMC will review interim data for adverse events and serious adverse events. The DSMC will use the Haybittle-Peto boundary with a difference of at least 3 standard errors in the analysis of serious adverse events (e.g. death

from all causes, aspiration pneumonia within the first 50 days post injury) needed to justify halting, or modifying the study before the planned completed recruitment. There will be no interim analyses for efficacy.

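### Non-serious adverse events are recorded only if attributed to the intervention, so they cannot be compared between conditions, and the rule contradicts the synopsis

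*Protocol*

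**What the plan says.** Section 13.1 of the protocol first defines an adverse event (AE) broadly, as any untoward medical occurrence whether or not the intervention caused it. It then narrows what is kept: "only those events which are possibly, probably or definitely attributable to the intervention will be noted". Section 10.6 repeats the restriction ("AEs that are possibly, probably or definitely attributable to the intervention will be reported via the eCRF as they occur"), and so does section 13.3 ("Other adverse events possibly, probably, or definitely attributable to the intervention will be recorded from the time of consent").

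The synopsis, under safety parameters, states no restriction: "Adverse events and serious adverse events will be collected for all participants".

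SAEs are handled differently. Section 13.3 says "All SAEs will be recorded from the time of consent until the final follow up visit at week 26", with no attribution condition. Section 13.2, however, defines an SAE as a kind of AE and follows directly on the filtered rule in 13.1.

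The data are used in three places:
- **Section 16.4.2, Safety.** SAE counts are compared between conditions. In addition, "Logistic regression will be used to compare binary adverse events (e.g. death" being the only example given.
- **Section 16.4.2, Interim analyses.** "The DSMC will review interim data for adverse events and serious adverse events". The Haybittle-Peto boundary of 3 standard errors is applied to SAEs.
- **Section 14.3.** The number or severity of adverse events, not only serious ones, is a ground for ending the study early.

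On who decides attribution, section 13.6.2 says "The blinded assessor is obligated to assess the relationship between study treatment and the occurrence of each AE/SAE".

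**The concern.** A record filtered by attribution to the intervention does not measure the same thing in the two conditions. Under section 11.1.2, a participant recruited during a site's control period gets no coordinator service, even after transfer to a region that has one. An event in such a participant can hardly be judged attributable to the intervention. The same event in the intervention phase can be, and is then recorded. A table of non-serious AEs by condition would tend to show an excess under the intervention even if the true incidence were equal.

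Three things are at stake:
- The synopsis and the body of the protocol tell sites different things about what to collect.
- The phrase on binary adverse events in section 16.4.2 is open enough to admit filtered data into a between-condition test, and the safety committee sees AEs as well as SAEs.
- The filter depends on a causality grade from the blinded assessor, the role that Appendix 1 also makes responsible for the EuroQol-5D-3L, the primary outcome instrument.

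A later analysis plan cannot repair this, because events that were never recorded cannot be recovered.

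**Working it through.** The protocol states no AE rate, so there is no figure of its own to reproduce. The check is mainly a comparison of the rules.

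**1. What is recorded, by type of event**

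| Source | Non-serious AEs | SAEs |
|---|---|---|
| Synopsis | all participants, no filter | all participants, no filter |
| Section 10.6 | only if attributable | reported, no filter stated |
| Section 13.1 | only if attributable | filtered too, if read literally with 13.2 |
| Section 13.3 | only if attributable | all, consent to week 26 |

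For non-serious events, three sections agree with each other and disagree with the synopsis. For SAEs, section 13.3 is explicit, and only the literal reading of 13.1 with 13.2 conflicts with it.

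**2. Whether the grades can apply in a control period**

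The scale in section 13.6.2 asks the assessor to weigh the timing of the event against the treatment period. The probable grade requires the event to abate when treatment stops. The definite grade refers to timing from the start of treatment or to reappearance when it is reintroduced. Neither can sensibly be given when there was no treatment. The possible grade could still be given by an assessor who does not know the phase. Control-phase counts are therefore near zero if the phase is known and arbitrary if it is not.

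**3. Whether the phase is known**

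Section 16.4.2, Blinding, expects assessors in rural areas to know their hospital's phase and concludes that assessors cannot be blinded to the intervention. Sections 10.2.2 and 10.2.3 nevertheless bring in a separate assessor for the coordinator questionnaire, in order to protect the main assessor's blinding. Asking that main assessor whether events were caused by the intervention works against this safeguard.

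**4. Illustration of size (hypothetical)**

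Figure 1 has 4 site pairs and 6 data-collection periods. Pairs cross over after periods 1, 2, 3 and 4.
- Control pair-periods: 1 + 2 + 3 + 4 = 10.
- Intervention pair-periods: 24 − 10 = 14.
- The total of 312 (section 16.3) over 24 pair-periods is 312 / 24 = 13 each.
- Control: 10 × 13 = 130. Intervention: 14 × 13 = 182.

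Assume the same true risk of a non-serious AE in both phases. Recorded count = risk × share attributed × number of participants, rounded. The share attributed in the intervention phase is assumed to be 25%. The p-values are from two-sided Fisher exact tests of 182 against 130.

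| Assumed true risk | Intervention, 25% attributed | Control, 0% attributed | p | Control, 25% attributed | p |
|---|---|---|---|---|---|
| 10% | 4.55 → 5 | 0 | 0.078 | 3.25 → 3 | 1.0 |
| 20% | 9.1 → 9 | 0 | 0.012 | 6.5 → 6 | 1.0 |
| 30% | 13.65 → 14 | 0 | 0.0005 | 9.75 → 10 | 1.0 |

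The true risk is equal in every row. What moves the result is whether attribution differs by phase.

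**The case against.** The strongest reply is that the comparisons the protocol actually plans do not use the filtered data. Section 13.3 records all SAEs. Section 16.4.2 compares SAE counts and names only death as a binary event, and death is an SAE. The only numerical halting rule is applied to SAEs. No comparison of non-serious counts is expressly planned. All of this stands. A reader might infer that the trial cannot compare harms between conditions at all; the documents do not support that.

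A reader might also infer that control-phase counts are zero by rule. No section says so. Participants in both phases are asked about events at weeks 12 and 26, and a truly blind assessor could grade a control-phase event as possible. Near zero or arbitrary is as far as the text goes.

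The illustrative p-values follow wholly from assuming 25% attribution in one phase and none in the other. With equal attribution they vanish, and the protocol plans no such test. They show a mechanism and do not predict a result.

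On the SAE definition, the filter in 13.1 governs what is noted rather than what an AE is, and grades for unrelated events would be redundant if unrelated SAEs were dropped. So 13.3 is clearly the intended rule. What remains is a conflict of wording that a site could misread.

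Finally, attribution-limited recording is a defensible choice for a training and support intervention. That is fair, but it makes the data descriptive, and neither the synopsis nor section 16.4.2 says so.

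**Conclusion.** The point holds in a limited form. Non-serious AEs are filtered by attribution in sections 10.6, 13.1 and 13.3. This contradicts the synopsis, and those events cannot validly be compared between conditions. The planned comparison of SAEs and deaths, and the committee's boundary, are unaffected provided section 13.3 governs; the literal reading of 13.1 with 13.2 conflicts with it and should be reconciled.

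The size cannot be derived from the documents. Under the stated assumptions the spurious contrast runs from 5 against 0 to 14 against 0, and there is none if attribution is equal in both phases. The direction rests on one assumption: that events are attributed more often in the intervention phase. That is likely, because the protocol itself concedes that assessors cannot be blinded. The point should be corrected, but it does not undermine the main safety analysis.

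**What to change.** 1. In section 16.4.2, Safety, limit the binary adverse events, and all between-condition safety comparisons including any supplied to the safety committee, to SAEs and deaths. Report attributable non-serious AEs descriptively, for the intervention phase only. Align the synopsis sentence with sections 10.6, 13.1 and 13.3.
2. State in sections 13.1 and 13.2 that the attribution filter applies only to non-serious events, as section 13.3 implies.
3. Reconcile sections 13.5 and 13.6.2 with the blinding safeguard in sections 10.2.2 and 10.2.3. One option is for the site investigator, who already grades intensity under section 13.6.1, to grade causality as well. Most investigators will know the phase, so this ties the filter more closely to it. That is acceptable only once attributable non-serious events are descriptive, so this step depends on the first.

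The cost is protocol wording, with no new data or staff. The downside is that non-serious AEs become descriptive.
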